12.7.2 Every 4 Weeks

Every 4 weeks (Weeks 40, 44, 48, and 52), the following procedures will be performed:

- Exploratory biomarker assessments
- Blood chemistry, haematology, coagulation screen, and CRP (refer to Table 9.7.8.2.1)
- Urine Tests (refer to Table 9.7.8.2.1)
- AAV5 antibody titer
- VWF:Ag
- PCR of vector DNA in blood, saliva, urine, semen, and stools
 - Sample testing during Safety Follow-Up is not required if at least 3 consecutive samples are clear during the Post-Infusion Follow-Up period. Subjects who have not had 3 consecutive negative samples by Week 52 should continue to have PCR testing every 4 weeks until 3 consecutive negative samples are documented (or upon consultation between the Investigator and Medical Monitor).

12.7.3 Every 8 Weeks

Every 8 weeks (Weeks 44 and 52), the following procedure will be performed:

- PBMC collection
- FVIII antibody titer

12.7.4 Week 38 and 52

At Week 38 and Week 52, the following procedure will be performed:

• Direct Thrombin test

12.7.5 Week 52

At Week 52, the following procedure will be performed:

- Haemo-QoL-A QoL assessment
- Weight

12.8 Safety Follow-Up – Years 2-5

Subjects who do not respond to BMN 270 treatment (ie, treatment failure, manifesting as either failure to achieve FVIII activity ≥ 5 IU/dL by Week 52 or inability to maintain independence from prophylactic FVIII replacement therapy due to joint bleeding episodes, in the judgment of the Investigator) may, at the Investigator's discretion and after discussion with the Medical Monitor, follow an abbreviated visit schedule after Week 52 of the study by attending only the Q12W and End of Year visits during Years 2-5.

Subjects who meet the definition of treatment failure and wish to follow an abbreviated schedule but who have not cleared vector shedding from all fluids must still provide samples for assessment every 4 weeks (during Year 2) or every 6 weeks (during Years 3-5) until vector shedding has cleared (but do not have to perform other scheduled assessments at those study visits).

During Years 2-5 of Safety Follow-up, the following procedures will be completed:

12.8.1 Year 2 – Every 4 Weeks (not required for treatment failure)

During Year 2, every 4 weeks (\pm 2 weeks), the following procedures will be performed:

- Assessment of Adverse Events and Concomitant Medications (including review of subject diary for bleeding and FVIII use)
- Liver Tests (refer to Table 9.7.8.3.1) local laboratory assessment
 - LTs may be monitored more or less frequently (and in particular when ALT values are >1.5x ULN) based on discussion between the Medical Monitor and the Investigator and review of subject data.
- FVIII activity level local laboratory assessment
 - FVIII activity level (one-stage clotting assay)
 - FVIII activity level (chromogenic substrate assay)

- Liver Tests (refer to Table 9.7.8.3.1) central laboratory assessment
 - LTs may be monitored more or less frequently (and in particular when ALT values are >1.5x ULN) based on discussion between the Medical Monitor and the Investigator and review of subject data.
- FVIII Assays central laboratory assessment
 - FVIII activity level (one-stage clotting assay)
 - FVIII activity level (chromogenic substrate assay)
 - FVIII coagulation activity exploratory assay
 - o Bethesda assay (with Nijmegen modification) for FVIII inhibitor level
 - FVIII antigen (ELISA)

Note: If a subject has used FVIII within 72 hours of a measurement day, all efforts should be made to obtain FVIII activity measurements when a 72-hour interval without FVIII use is achieved; the 72-hour wash-out period is only intended for subjects who have achieved FVIII \geq 5 IU/dL at 16 weeks after BMN 270 infusion and who have not resumed standard of care FVIII replacement therapy.

- PCR of vector DNA in blood, saliva, urine, semen, and stools (if required)
 - Sample testing during Year 2 is not required if at least 3 consecutive samples are negative during the Post-Infusion Follow-Up period in Weeks 1-52.
 Subjects who have not had 3 consecutive negative semen samples by Week 52 should continue to have PCR testing of semen every 4 weeks during Year 2 until 3 consecutive negative samples are documented (or upon consultation between the Investigator and Medical Monitor).
 - Subjects who meet the definition of treatment failure and wish to follow an abbreviated schedule but who have not cleared vector shedding from all fluids must still provide samples for assessment every 4 weeks during Year 2 until vector shedding has cleared (in such a case, these subjects do not need to perform other assessments except for PCR sample delivery scheduled at these timepoints).

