PBMC Collection (for determination of FVIII and Capsid specific CTL activity)	X				Х			Х	
Von Willebrand Factor Antigen (VWF:Ag)	Х				2	X		Х	
PCR of vector DNA in blood, saliva, urine, semen, and stools ^e	Xe	Xe	Xe		Σ	Ke		Х	
Exploratory biomarker assessments ^g	Х				2	X		Х	
Haemo-QoL-A QoL assessment	Xf				Σ	ζf		Х	

Table 9.1.5: Schedule of Events – Safety Follow-Up (Years 2-5)

* Visit windows are ± 2 weeks for visits in Years 2-5. The Q6W visits during Years 3-5 should restart after each End of Year visit (eg, the first Q6W visit during Year 3 should be ~6 weeks after the End of Year 2 visit).

^a Complete physical examination should be performed at the End of Year visits; brief physical examination may be performed at other study visits. Weight should be recorded at the second Q12W visit each year and at every End of Year visit during Years 2-5.

Proprietary and Confidential

31 January 2019

^b Refer to Table 9.7.8.2.1 for laboratory assessments to be included, and to Table 9.7.8.3.1 for liver tests. LTs may be monitored more or less frequently (and in particular when ALT values are $\geq 1.5x$ ULN) based on discussion between the Medical Monitor and the Investigator and review of subject data, but LTs will be monitored at least twice weekly during periods when a subject's ALT is $\geq 3x$ ULN. Patients with ALT $\geq 1.5x$ ULN during the study may undergo additional evaluations (eg, imaging studies including MRI or ultrasound, additional blood tests, and/or liver biopsy) at the discretion of the investigator. Additional testing of FVIII and LTs during any study week may be performed if: (1) the ALT has increased to above ULN or increased by > 10 U/L from prior assessment; (2) Increases in ALT values from prior assessment are accompanied by declines in FVIII activity level; or after a discussion between the Medical Monitor and the Investigator based on a review of subject data. If FVIII levels and/or ALT values are stable over the course of several weeks, assessment of FVIII activity and ALT levels may be adjusted based on discussion between the Medical Monitor and the Investigator between the Medical Monitor and the Investigator. During Years 2-5 of the Post-Infusion Follow-Up period, urine tests and blood, chemistry, and coagulation tests should be performed at the second Q12W visit each year and at every End of Year visit.

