- ^e Sample testing during Safety Follow-Up is not required if at least 3 consecutive samples are cleared during the Post-Infusion Follow-Up period. Subjects who have not had 3 consecutive negative samples by Week 52 should continue to have PCR testing every 4 weeks (during Year 2) or every 6 weeks (during Years 3-5) until 3 consecutive negative samples are documented (or upon consultation between the Investigator and Medical Monitor).
- ^fHaemo-QoL-A QoL assessment during Years 2-5 of Safety Follow-up should be performed at the second Q12W visit each year and at every End of Year visit.
- ^g Blood samples will be collected to evaluate biochemical, molecular, cellular, and genetic/genomic aspects relevant to hemophilia A, coagulation, and/or AAV gene transfer, and to develop assays used for these evaluations. Subjects may choose to opt out of the exploratory genetic/genomic research being done to study or try to discover genes that are not yet known to be associated with hemophilia A. While exploratory samples will be collected at the time points indicated above, testing of these samples (including any other exploratory assessments) will be performed only as deemed necessary by the Sponsor.
- ^h Subjects who meet the definition of treatment failure to BMN 270 therapy after Week 52 may omit the Q4W and Q6W visits during Years 2-5, and must attend only the Q12W and End of Year visits. Such subjects following the abbreviated schedule who have not yet cleared vector shedding in all fluids must still provide samples Q4W (during Year 2) or Q6W (during Years 3-5) until vector shedding has been cleared (but do not need to do other scheduled assessments at those visit dates).

270-201 Amendment 8

					Steroid T	reatment	Period ^d					Post-Steroid Period ^c					
	Week 1	Week 2	Week 3	Week 4	Week 5	Week 6	Week 7	Week 8	Week 9	Week 10	Week 11 ^b	Week 1	Week 2	Week 3	Week 4	Week 13	
Therapeutic corticosteroids (dose in mg/day) ^a	60 mg	60 mg	40 mg	40 mg	30 mg	30 mg	20 mg	20 mg	15 mg	10 mg	5 mg						
FVIII activity testing												Х	Х	Х	Х		
Liver testing												Х	Х	Х	Х		
Hepatitis B testing ^e						Х						Х				Х	
HCV Viral Load ^e						Х						Х				Х	

Table 9.1.6: Schedule of Events – Therapeutic Corticosteroids for LT Elevations

^a Therapeutic corticosteroids may be initiated when a subject's ALT value is ≥ 1.5x ULN or based on review of FVIII and liver enzyme data after consultation between the Investigator and the Medical Monitor.

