9.6 Dietary or Other Protocol Restrictions

There are no dietary or other protocol restrictions for this study.

Subjects should be advised to abstain from any blood or sperm donation after BMN 270 infusion, until there is no further evidence of vector shedding from PCR analysis of samples.

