9.7.8.6 Vector Shedding

Vector shedding has been extensively studied in all similar clinical trials performed to date. (Nathwani, 2014, N.Engl.J.Med.); (Manno, 2006, Nat.Med.); (Schenk-Braat, 2007, J.Gene Med.); (Croteau, 2004, Ann.Occup.Hyg.). In the literature referenced above, including Haemophilia B clinical studies utilizing AAV2 and AAV8, vector was no longer detectable after 40 days in blood, saliva, urine or stool, but in one study was detected in the seminal fluid but not in motile sperm (Manno, 2006, Nat.Med.). In these studies, the amount of vector present in these bodily fluids involved an extremely small fraction of the infused dose. More recent data from an ongoing AAV-FIX study demonstrates persistence of the vector in both the blood and the semen for at least 39 weeks (Miesbach, 2016, Haemophilia).

During the Post-Infusion Follow-Up period, subjects will undergo testing of various bodily samples to look for evidence of vector shedding for possible viral transmission. Bodily

fluids will be tested by PCR at the time points indicated in Table 9.1.2, Table 9.1.3, Table 9.1.4, and Table 9.1.5. Fluids tested will include:

- Blood
- Saliva
- Semen
- Urine
- Stool

Vector shedding will also be extensively studied in the present clinical trial, every other week between Weeks 4-16, then every 4 weeks to Week 52 until at least 3 consecutive negative results are obtained. Testing of semen will continue through Week 12, even if 3 consecutive negative results have been recorded in that compartment prior to that timepoint. Subjects who have not had 3 consecutive negative samples by Week 52 should continue to have PCR testing every 4 weeks until 3 consecutive negative samples are documented (or upon consultation between the Investigator and Medical Monitor). Subjects who meet the definition of treatment failure and wish to follow an abbreviated schedule (refer to Section 12.5.3 but who have not cleared vector shedding from all fluids must still provide samples for assessment until vector shedding has cleared: every 4 weeks (during Year 2), or every 6 weeks (during Years 3-5).

Contraception use may need to be extended beyond 26 weeks in individual subjects based on observed vector shedding in semen. After 6 months, subjects may stop contraception use only if they have had 3 consecutive negative semen samples (upon consultation between the Investigator and Medical Monitor).

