12.8.2 Years 3-5 – Every 6 Weeks (not required for treatment failure)

During Years 3-5, every 6 weeks (± 2 weeks), the following procedures will be performed:

- Assessment of Adverse Events and Concomitant Medications (including review of subject diary for bleeding and FVIII use)
- Liver Tests (refer to Table 9.7.8.3.1) local laboratory assessment

- LTs may be monitored more or less frequently (and in particular when ALT values are >1.5x ULN) based on discussion between the Medical Monitor and the Investigator and review of subject data.
- FVIII activity level local laboratory assessment
 - FVIII activity level (one-stage clotting assay)
 - FVIII activity level (chromogenic substrate assay)
- Liver Tests (refer to Table 9.7.8.3.1) central laboratory assessment
 - LTs may be monitored more or less frequently (and in particular when ALT values are >1.5x ULN) based on discussion between the Medical Monitor and the Investigator and review of subject data.
- FVIII Assays central laboratory assessment
 - FVIII activity level (one-stage clotting assay)
 - FVIII activity level (chromogenic substrate assay)
 - FVIII coagulation activity exploratory assay
 - Bethesda assay (with Nijmegen modification) for FVIII inhibitor level
 - FVIII antigen (ELISA)

Note: If a subject has used FVIII within 72 hours of a measurement day, all efforts should be made to obtain FVIII activity measurements when a 72-hour interval without FVIII use is achieved; the 72-hour wash-out period is only intended for subjects who have achieved FVIII \geq 5 IU/dL at 16 weeks after BMN 270 infusion and who have not resumed standard of care FVIII replacement therapy.

- PCR of vector DNA in blood, saliva, urine, semen, and stools (if required)
 - Sample testing during Years 3-5 is not required if at least 3 consecutive samples are negative during the Post-Infusion Follow-Up period in Weeks 1-52 and/or Year 2. Subjects who have not had 3 consecutive negative semen samples by Week 52 should continue to have PCR testing of semen every 6 weeks during Years 3-5 until 3 consecutive negative samples are documented (or upon consultation between the Investigator and Medical Monitor).

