Note: If a subject has used FVIII within 72 hours of a measurement day, all efforts should be made to obtain FVIII activity measurements when a 72-hour interval without FVIII use is achieved; the 72-hour wash-out period is only intended for subjects who have achieved FVIII \geq 5 IU/dL at 16 weeks after BMN 270 infusion and who have not resumed standard of care FVIII replacement therapy.

- Vital Signs
- Blood chemistry, haematology, coagulation screen, and CRP (refer to Table 9.7.8.2.1)
 - ABO blood typing assessment should be performed at the next regularly scheduled study visit (or at least prior to the end of the subject's participation in the study)
- Urine Tests (refer to Table 9.7.8.2.1)
- AAV5 antibody titer
- FVIII antibody titer
- PBMC collection
- VWF:Ag
- Exploratory biomarker assessments
- Haemo-QoL-A QOL assessment (at Week 76, Week 128, Week 180, Week 232, and End of Year visits only)
- PCR of vector DNA in blood, saliva, urine, semen, and stools (if required)
 - Sample testing during Years 2-5 is not required if at least 3 consecutive samples are negative during the Post-Infusion Follow-Up period in Weeks 1-52. Subjects who have not had 3 consecutive negative semen samples by Week 52 should continue to have PCR testing of semen every 4 weeks (during Year 2) or every 6 weeks (during Years 3-5) until 3 consecutive negative samples are documented (or upon consultation between the Investigator and Medical Monitor).

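### After Week 52 the protocol gives conflicting rules on which fluids stay under vector-shedding PCR, for whom and how often, and two frequencies for the laboratory panels

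*Protocol*

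**What the plan says.** Five fluids are tested for vector DNA: blood, saliva, semen, urine and stool. For the period after Week 52 the current text gives three kinds of rule.

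- **Any sample.** Table 9.1.5 footnote e states "Subjects who have not had 3 consecutive negative samples by Week 52 should continue to have PCR testing every 4 weeks (during Year 2", and moves to every 6 weeks in Years 3-5. Sections 9.7.8.6 and 12.7.2 say that such subjects "should continue to have PCR testing every 4 weeks until 3 consecutive negative samples are documented", with no change of interval at Year 3. None of the three is limited to semen.
- **Semen.** Section 12.8.1 states "Subjects who have not had 3 consecutive negative semen samples by Week 52 should continue to have PCR testing of semen every 4 weeks" for Year 2. Section 12.8.2 says that these subjects "should continue to have PCR testing of semen every 6 weeks during Years 3-5 until 3 consecutive negative samples are documented". Section 12.8.3 says that they "should continue to have PCR testing of semen every 4 weeks (during Year 2) or every 6 weeks (during Years 3-5".
- **All fluids.** Section 12.8.1 requires treatment failures who wish to follow the abbreviated schedule and "who have not cleared vector shedding from all fluids must still provide samples for assessment every 4 weeks during Year 2". Sections 12.8 and 12.8.2 carry the matching rule for Years 3-5.

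Section 9.6 ties an instruction to subjects to these results: they are advised against donating blood or sperm "until there is no further evidence of vector shedding from PCR analysis of samples".

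On a separate matter, Table 9.1.5 footnote b says that urine, chemistry and coagulation tests in Years 2-5 "should be performed at the second Q12W visit each year and at every End of Year visit". Section 12.8.3 lists the same tests at every 12-week and End of Year visit.

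**The concern.** Sites work from the schedule table and from Section 12. Here the two do not give the same instruction. A site that follows the explicit continuation sentence in 12.8 would keep testing semen and could stop testing blood, saliva, urine or stool in a subject who is still positive in one of those fluids. A site that follows the table would carry on. A treatment failure on the abbreviated schedule with the same results must keep supplying samples under 12.8 itself. The completeness of shedding data could then depend on the site and on whether the subject was classed as a treatment failure, and the protocol gives no reason for either.

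Shedding is a safety outcome, and the donation advice depends on PCR evidence. Blood bears directly on that advice but is absent from the continuation sentence. Late positivity is plausible on the protocol's own account: Section 9.7.8.6 cites a related factor IX vector study in which vector persisted in blood and semen for at least 39 weeks.

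**Working it through.** The plan states no figure on this point that could be reproduced. The check sets the current rules side by side.

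| Place | Fluids that continue after Week 52 | Interval, Year 2 | Interval, Years 3-5 |
|---|---|---|---|
| Table 9.1.5 footnote e | any not cleared | 4 weeks | 6 weeks |
| 9.7.8.6 (general rule) | any not cleared | 4 weeks | 4 weeks (no change stated) |
| 12.7.2 | any not cleared | 4 weeks | 4 weeks (no change stated) |
| 12.8.1 to 12.8.3, continuation sentence | semen | 4 weeks | 6 weeks |
| 12.8, 12.8.1, 12.8.2 and 9.7.8.6, failures on abbreviated schedule | all not cleared | 4 weeks | 6 weeks |

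**Fluids.** Take a full-schedule subject who has cleared semen by Week 52 but is still positive in blood. Blood tests in Year 2:

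- Table 9.1.5 footnote e, 9.7.8.6 and 12.7.2: up to 52/4 = 13, stopping earlier at three consecutive negatives or after consultation with the Medical Monitor.
- Continuation sentence of 12.8.1 alone: 0.
- PCR bullet and exemption sentence of 12.8.1 read together: up to 13. The bullet names all five fluids where required, and the exemption for three consecutive negatives is not limited to semen.
- Treatment failure on the abbreviated schedule with the same results: up to 13.

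The exemption sentence does not say that the three negatives must be in the same fluid. Table 9.1.3 footnote e does speak of each matrix, but it covers Weeks 17-32 only. Section 12.8 can therefore be read either way.

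**Interval in Years 3-5.** Every 4 weeks gives 52/4 = 13 samples a year; every 6 weeks gives 52/6 = 8.7, about 9. Both are maxima. Section 9.7.8.6 also differs within itself: its general rule stays at 4 weeks, while its rule for failures on the abbreviated schedule changes to 6.

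**Clearance window for the exemption.** Section 12.8.2 waives testing in Years 3-5 if the three negatives fell in Weeks 1-52 and/or Year 2. Section 12.8.3, which covers visits in the same years, counts Weeks 1-52 only. A subject who first clears in Year 2 meets the first exemption and not the second.

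**Laboratory panels, Years 2-5.** Section 12.8.3 lists four visits a year (in Year 2: Weeks 64, 76, 88 and 104). Footnote b selects the second 12-week visit and the End of Year visit (Weeks 76 and 104), so 2 a year, or 2 × 4 = 8 over Years 2-5. Section 12.8.3 gives 4 a year, or 4 × 4 = 16. That section restricts weight and quality of life to named visits but places no such limit on the panels.

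**The case against.** The best reply is that Section 12.8 should be read as a whole. Its PCR bullet names all five fluids, its exemption is general, and a subject still positive in blood does not meet that exemption. The semen sentence could then be emphasis added to a general rule. Table 9.1.5 marks the five-fluid PCR row at every visit type, and 9.7.8.6 and 12.7.2 agree with it. Semen also carries the most weight elsewhere, in the contraception rule and in the enrolment-halt criterion, and every passage continues semen testing.

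Much of this stands. It rules out several stronger conclusions that a reader might draw:

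- That positive blood, saliva, urine or stool would never be followed to clearance. This would happen only if a site applied the semen sentence alone.
- That every subject who is not a treatment failure is affected. Only those uncleared in a non-semen fluid at Week 52 are.
- That the donation advice would end too early. Without a new negative result the last evidence is positive, so the advice would be prolonged.
- That time to clearance would be censored. The protocol shown defines no such analysis.

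The reply does not remove the contradiction. The semen restriction appears in three consecutive subsections, and it is the only sentence there that says what must continue for subjects outside the abbreviated schedule. The general bullet applies only where testing is required. The Amendment 7 change summary does explain why six-weekly visits were thought sufficient in Years 3-5, but the current 9.7.8.6 and 12.7.2 still carry the 4-week rule without a change.

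**Conclusion.** The point holds as a contradiction in current text that affects which safety samples sites collect. For a full-schedule subject still positive in a non-semen fluid at Week 52, the documents support anything from 0 to 13 tests of that fluid in Year 2. In Years 3-5 the interval is 4 or 6 weeks, at most 13 or about 9 samples a year. The exemption window differs between 12.8.2 and 12.8.3. Laboratory panels are due 2 or 4 times a year.

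The number of subjects affected cannot be derived. The protocol gives no count of subjects uncleared in a non-semen fluid at Week 52, and enrolment is capped at 15. The test counts assume full attendance and no earlier stop. The consequence for blood, saliva, urine and stool depends on how a site reads 12.8, and is a risk of uneven follow-up and not an established loss. Correction is worthwhile because it is specific and cheap, and because a statistical analysis plan cannot recover samples that were never taken.

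**What to change.** The sponsor should reconcile Sections 9.7.8.6, 12.7.2 and 12.8.1 to 12.8.3 with Table 9.1.5 footnotes b and e. One shedding rule, worded the same in each place, should state:

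- which fluids continue after Week 52;
- for which subjects, including whether those on the full and abbreviated schedules differ and, if so, why;
- at what interval in Year 2 and in Years 3-5;
- when a fluid counts as cleared, and over which period the negative results may fall.

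One frequency for chemistry, coagulation and urine tests in Years 2-5 should stand in both footnote b and 12.8.3. In the same edit, the reference in 9.7.8.6 to Section 12.5.3 for the abbreviated schedule should be corrected, since 12.5.3 is the Day 8 visit and the abbreviated schedule is described in 12.8.

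This review does not say which rule is right. The cost is a protocol clarification. If the broader shedding rule is the one intended, some subjects would give a few more PCR samples, in Year 2 at visits already scheduled.
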